6.2 Dose Modification

6.2.1 Dose-cohort Study Escalation/De-escalation and Stopping Rules

6.2.1.1 Dose-exploration

The dose-exploration part of the study will estimate the MTD/RP2D of AMG 160 in NSCLC. The starting dose of AMG 160 will be 1 dose level below the RP2D or otherwise the highest dose level deemed safe and tolerable as determined in the phase 1 monotherapy study (20180101; planned dose levels show in [Table 6-2](#)).

Table 6-2. Study 20180101 Planned Doses per Dose Cohort Level

Cohort Number	Dose (mg) IV Every 2 Weeks
[REDACTED]	

IV = intravenous

Dose Level Determination

Dose exploration will begin with 2 to 4 subjects. The study DLT window is 28 days (see Section [6.2.1.3](#)). To be DLT evaluable, subjects must receive all planned cycle 1 doses of AMG 160. After a minimum of 2 subjects enrolled at a certain dose level are DLT

evaluative, a DLRT meeting will be convened. Depending on observed safety data, the following may occur:

1. additional enrollment to dose Level 1; or
2. dose de-escalation to 1 dose below the starting dose; or
3. alternative dosing schedules, including further dose escalation, as per the ongoing mCRPC trial (Study 20180101), may be explored based on emerging safety and PK data.

Rules for dose-escalation/de-escalation are derived using a modified toxicity probability interval (mTPI) model with a target toxicity probability of 0.28.

Dose level decisions are made based on this posterior probability of toxicity, using 3 toxicity probability intervals (TPI):

- under-dosing TPI: DLT rate from 0 to < 23%
- target TPI: DLT rate from 23% to 33%, inclusive
- over-dosing: DLT rate > 33%

For the current dose level and after adjusting for the width of the under-dosing TPI, if the DLT rate is most likely in the under-dosing TPI then the recommendation is to dose escalate or stay at the current level. If the DLT rate is most likely in the target TPI then the recommendation is to stay at the current level. If the DLT rate is most likely in the over-dosing TPI then the recommendation is to de-escalate. If DLTs are observed, the MTD is the dose level with a DLT toxicity rate closest to 28%.

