4.2.1 Replacement of Subjects

Subjects who discontinue from the study prior to completing the DLT assessment window for reasons other than a DLT will be considered non evaluable for dose escalation decisions and MTD determination and may be replaced by an additional

subject at that same dose level, as necessary, to ensure that all dose escalation decisions are made with sufficient safety data (eg, safety data from at least 2 evaluable subjects in a multi subject cohort).

Subjects who receive supportive care during the DLT assessment window that confounds the evaluation of DLTs may be replaced at the discretion of the medical monitor or DLRT.

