6.2.1.3 Dose-limiting Toxicity

Dose-limiting toxicities are defined as any adverse event with an onset within first 28 days following first dose of AMG 160 with any of the following criteria unless clearly attributable to causes other than AMG 160 treatment:

- grade 5 toxicity (eg, death not due to disease progression)
- grade 3 adverse event lasting more than 3 days (with the exception of fatigue)
- grade 4 adverse event regardless of duration

- grade 3 nausea, vomiting, or diarrhea that do not improve to grade ≤ 1 within 72 hours despite maximum supportive care
- grade ≥ 3 neurologic events that do not improve to grade ≤ 1 within 7 days with treatment interruption and routine medical management
- grade 3 febrile neutropenia that cannot be attributed to CRS
- AST or ALT values of $> 3 \times$ ULN AND with serum TBL level of $> 2 \times$ ULN without signs of cholestasis or there is no other clear alternative to explain the observed liver-related laboratory abnormalities (ie, criteria for Hy's Law indicative of severe drug-induced liver injury [DILI])
- grade 4 neutropenia lasting > 7 days
- grade 4 thrombocytopenia lasting > 7 days
- grade 3 or higher thrombocytopenia with clinically significant bleeding regardless of duration of thrombocytopenia
- grade 4 anemia
- grade 4 non-hematologic laboratory abnormality of any duration

The following adverse events will NOT be adjudicated as DLT regardless of the duration:

- lymphopenia or lymphocyte count decreased of any grade
- grade 3 fever (defined as a temperature $\geq 40^\circ\text{C}$ with a duration of ≤ 24 hours) occurring outside the context of CRS
- laboratory parameters of grade ≥ 3 , not considered clinically relevant, and improved to grade ≤ 2 within 72 hours.
- grade ≥ 3 transaminitis associated with CRS that resolves to grade ≤ 1 within 5 days

Determination of whether a subject is evaluable for DLT assessment will be made in accordance with the following rules:

- Subjects who receive study treatment and remain on study through the DLT assessment window will be considered DLT-evaluable.
- Subjects who do not complete safety assessments during the DLT assessment window for reasons other than a DLT will be considered nonevaluable for dose escalation decisions and MTD determination and may be replaced by an additional subject at that same dose level.

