9.3 Analysis Sets, Subgroups, and Covariates

9.3.1 Analysis Sets

The analysis of all endpoints, unless noted otherwise, will be conducted on the Safety Analysis Set defined as all subjects that are enrolled and receive at least 1 dose of AMG 160.

The analysis of DLT will be conducted on the DLT Analysis Set defined as all subjects that are enrolled and receive at least 1 dose of AMG 160 with an evaluable DLT endpoint. The DLT endpoint is evaluable if either: 1) the subject experiences a DLT; or 2) the subject does not experience a DLT after receiving all planned doses within the 28-day DLT window in cycle 1.

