9.4.1 Planned Analyses

9.4.1.1 Interim Analysis and Early Stopping Guidelines

Safety data will be reviewed on an ongoing basis.

During dose exploration and formally during DLRMs, Amgen, in consultation with the site investigators, will review all available cumulative data by cohort prior to making dose escalation or dose de-escalation recommendations. Adverse events and DLTs observed in all subjects will be evaluated continually and fully integrated into all DLRMs and considered in all enrollment and dosing decisions. During dose expansion, Amgen will conduct evaluations of the ongoing grade 4 or higher treatment-related adverse event rate to assess if the threshold for possible early trial termination has been reached. If this threshold is met, enrollment to dose expansion will be halted pending review of safety data by the DLRT. After receiving the DLRT recommendation, Amgen will choose to take one of the following actions.

- 1) Terminate the trial

- 2) Amend the protocol to potentially improve the benefit/risk for subjects (eg, increase safety monitoring, modify dose/schedule, mandate [REDACTED])
- 3) Continue dose expansion without any changes

The stopping rules use a Bayesian approach proposed by Thall et al, 1995 to terminate the study if the posterior probability that the grade 4 or higher treatment-related adverse event rate is greater than 20% is $> 80\%$. The stopping boundaries assume a prior distribution of Beta (0.40, 1.60) are presented in [Table 9-1](#) and the operating characteristics with pre-specified batch size of 10 new subjects per batch are presented in [Table 9-2](#). The operating characteristics in [Table 9-2](#) provide the probability of stopping the trial early for given hypothetical true rate of grade 4 or higher treatment-related adverse events, whereas the stopping criteria in [Table 9-2](#) are based on situations where the empirical evidence would result in a posterior probability of $\geq 80\%$ that the true grade 4 or higher treatment-related adverse event rate is $\geq 20\%$.

Table 9-1. Stopping Boundary for Dose Expansion With Posterior Probability of 80% and Grade 4 or Higher Treatment-related Adverse Event Limit of 20%

Number of Subjects	Stop Study if Observing These Many Grade 4 or Higher Treatment-related Adverse Events
10	≥ 4
20	≥ 6
30	≥ 9
40	Dose Expansion Complete

Table 9-2. Operating Characteristics With Batch Size of 10 Subjects

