6.3 DLT Analysis Set

The analysis of DLT will be conducted on the DLT Analysis Set defined as all subjects that are enrolled and receive at least 1 dose of AMG 160 with an evaluable DLT endpoint.

The DLT endpoint is evaluable if either:

- 1) the subject experiences a DLT; or
- 2) the subject does not experience a DLT after receiving all planned doses within the 28-day DLT window in cycle 1.

7. Planned Analyses

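### DLT evaluability is defined inconsistently: 6.2.1.1 and SAP 3.1 require every cycle 1 dose with no exception for a subject who has a DLT, and a missed dose without a DLT is handled two ways

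*Protocol*

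**What the plan says.** Evaluability for DLT is defined in several places, in three forms that are not equivalent.

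- **All doses, no exception.** Protocol 6.2.1.1, under dose level determination, and SAP 3.1: "To be DLT evaluable, subjects must receive all planned cycle 1 doses of AMG 160". The next sentence uses this term to count the two subjects needed to convene a dose level review.
- **Treated and followed.** Protocol 6.2.1.3: "Subjects who receive study treatment and remain on study through the DLT assessment window will be considered DLT-evaluable". No full dosing is required. A second rule there says that subjects with incomplete safety assessments "for reasons other than a DLT will be considered nonevaluable for dose escalation decisions and MTD determination". Protocol 4.2.1 has a matching replacement rule: "Subjects who discontinue from the study prior to completing the DLT assessment window for reasons other than a DLT will be considered non evaluable".
- **A DLT, or all doses without one.** Protocol 9.3.1: "The DLT endpoint is evaluable if either: 1) the subject experiences a DLT"; the alternative, as SAP 6.3 words it, is that "the subject does not experience a DLT after receiving all planned doses within the 28-day DLT window in cycle 1".

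Protocol 9.4.1.1 (and SAP 7.1) adds: "Adverse events and DLTs observed in all subjects will be evaluated continually and fully integrated into all DLRMs". SAP Section 10, on changes from the protocol, does not mention the differences, so the SAP carries the first and third forms side by side.

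**The concern.** The first form sits where the dose decision is described, and the subject it leaves out is a realistic one. A grade 4 adverse event is a DLT under 6.2.1.3 unless clearly due to another cause. Table 6-3 requires permanent discontinuation for grade 4 CRS, and CRS is the identified risk in Table 2-1. Cycle 1 has several infusions (for example days 1, 8 and 15 in Table 1-2). A subject stopped after an early one cannot have received every planned dose, so the sentence in 6.2.1.1, taken alone, makes that subject non-evaluable. If this were applied to the mTPI counts, it would bias the DLT rate downward.

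The second gap is also realistic. Under Table 6-3 an infusion interrupted for grade 2 CRS is not resumed, and under 6.2.2.1.1 a technical delay beyond 72 hours means the dose is skipped. Such a subject, without a DLT and still on study, is in the denominator under 6.2.1.3 and out of it under 6.2.1.1, 9.3.1 and SAP 6.3.

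The MTD or RP2D is a primary objective and is determined from very small cohorts.

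**Working it through.** **Inputs.** From 6.2.1.1 and Appendix 9: Beta(1,1) prior at each dose level, target rate 0.28, under-dosing below 0.23, target interval 0.23 to 0.33, over-dosing above 0.33. Decisions are from Table 11-3 (identical to SAP Table 3.1). Dose exploration begins with 2 to 4 subjects, and a review needs at least 2 evaluable subjects.

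**Step 1: reproduce the plan's table.** With x DLTs in n evaluable subjects the posterior is Beta(1+x, 1+n−x). For each interval, divide its posterior probability by its width (0.23, 0.10, 0.67); the largest value gives the decision. For 0/2, P(rate > t) = (1−t)^3, so:

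- under-dosing: (1 − 0.77^3)/0.23 = 0.5435/0.23 = 2.363
- target: (0.77^3 − 0.67^3)/0.10 = 0.1558/0.10 = 1.558
- over-dosing: 0.67^3/0.67 = 0.3008/0.67 = 0.449

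The decision is Escalate, as printed. The other cells used here:

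| DLTs/n | Under | Target | Over | Decision |
|---|---|---|---|---|
| 1/3 | 0.993 | 1.730 | 0.893 | Stay |
| 2/4 | 0.363 | 1.214 | 1.187 | Stay |
| 2/3 | 0.175 | 0.679 | 1.331 | De-escalate |

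The rule for DU (de-escalate and never return) has no stated cutoff. Assuming P(rate > 0.28) > 0.95, all 63 cells of Table 11-3 reproduce; with 0.90, 4 of 63 do not. The table itself is sound. The question is which subjects enter it.

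**Step 2: a DLT subject kept, or dropped because dosing stopped.**

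- Three treated, one DLT: 1/3 Stay; dropped, 0/2 Escalate.
- Four treated, one DLT: 1/4 Stay; dropped, 0/3 Escalate.
- Four treated, two DLTs: 2/4 Stay; both dropped, 0/2 Escalate.
- Three treated, two DLTs: 2/3 De-escalate; one dropped, 1/2 Stay.

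**Step 3: a subject without a DLT who missed a dose, counted (6.2.1.3) or not (6.2.1.1, 9.3.1, SAP 6.3).**

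- 2/4 Stay against 2/3 De-escalate.
- 3/5 De-escalate against 3/4 DU.
- 2/3 De-escalate against 2/2 DU.

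**Step 4: probability that the table says Escalate, four treated, no replacement.** Let q be the share of DLT subjects whose dosing stops and who are dropped. The documents give no value for q; 0, 0.5 and 1 are shown. Escalate arises only from no DLTs, one DLT dropped (0/3), or two DLTs both dropped (0/2). With true DLT rate p:

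P(Escalate) = (1−p)^4 + q·4p(1−p)^3 + q²·6p²(1−p)²

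- p = 0.33: terms 0.2015, 0.3970, 0.2933. q = 0: 20%. q = 0.5: 0.2015 + 0.1985 + 0.0733 = 47%. q = 1: 0.2015 + 0.3970 + 0.2933 = 89%.
- p = 0.28: terms 0.2687, 0.4180, 0.2439. q = 0: 27%. q = 0.5: 0.2687 + 0.2090 + 0.0610 = 54%. q = 1: 0.2687 + 0.4180 + 0.2439 = 93%.

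The values for q above 0 describe the literal reading of 6.2.1.1 applied to the mTPI counts, not how the plan as a whole would be expected to operate.

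**The case against.** A reader might infer that 6.2.1.1 is the definition used for dose decisions, and that the plan therefore directs DLT subjects to be dropped at the dose level review. The documents do not support that. Both 4.2.1 and the second rule in 6.2.1.3 are written for dose escalation decisions and MTD determination, and both exempt DLTs. Section 9.4.1.1 and SAP 7.1 bring DLTs in all subjects into every review. The sentence in 6.2.1.1 leads into the count that convenes a review and does not say that an observed DLT leaves the mTPI calculation. Escalation also needs a unanimous vote on all available data (Appendix 3).

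A reader might also infer that 9.3.1 and SAP 6.3 govern only the final table. That is not stated either: they apply to the analysis of DLT without limit of time, and SAP 9.6.1 places the mTPI estimate of DLT probability on the DLT Analysis Set.

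This answers the stronger reading but does not remove the contradiction. Sections 4.2.1 and 6.2.1.3 keep a DLT subject who did not finish the window only by implication, by saying who is not evaluable. Section 9.4.1.1 says DLTs are considered, not who enters the numerator and denominator. Only 9.3.1 and SAP 6.3 include the DLT subject in so many words, and they define an analysis set without mentioning dose level reviews. None of these texts settles the subject without a DLT who missed a dose.

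**Conclusion.** The point holds as a contradiction between stated rules. Protocol 6.2.1.1 and SAP 3.1 lack the DLT exception found in 4.2.1, 6.2.1.3, 9.3.1 and SAP 6.3, and the rules disagree on a missed dose without a DLT. Either difference can move the mTPI decision by a step at the cohort sizes planned: Stay to Escalate (1/3 against 0/2), or Stay to De-escalate (2/4 against 2/3).

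Those decisions come straight from Table 11-3 and need no assumption. The escalation probabilities (20% rising to 47% or 89% at a true DLT rate of 33%) rest on an assumed share of DLTs that stop dosing, on four treated subjects without replacement, and on the literal reading. They bound what is at stake and do not predict conduct. A careful review team would probably count the DLT; the plan should not leave that to its judgement. The stated mTPI table is not in error.

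**What to change.** Reconcile Protocol 4.2.1, 6.2.1.1, 6.2.1.3 and 9.3.1 and SAP 3.1 and 6.3 to one definition. State that it sets both the mTPI numerator and denominator at dose level reviews and the DLT Analysis Set.

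- Every subject with a DLT in the window counts, whatever doses were received.
- A subject without a DLT counts only after meeting one stated dosing requirement and completing safety follow-up through the 28-day window.

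Copying 9.3.1 over 6.2.1.3 would not be enough, because 9.3.1 does not expressly require staying on study and completing safety assessments to the end of the window. On the Table 1-2 schedule the last cycle 1 infusion is on day 15. A subject without a DLT who leaves on day 16 is non-evaluable under 4.2.1 and 6.2.1.3 but could count under 9.3.1. With two DLTs among four treated, that is 2/3 De-escalate against 2/4 Stay. The 6.2.1.3 follow-up requirement should therefore be kept.

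The cost is wording in the protocol and SAP; no change to the mTPI table or sample size is needed.

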6.2.1.2 Dose Expansion

If 1 or more OR are observed in dose exploration, dose expansion will be conducted to confirm the safety and tolerability of the selected dose and to further evaluate the efficacy of AMG 160. Dose modification may occur as a result of interim analyses as described in Section [9.4.1.1](#).

6.2.1.3 Dose-limiting Toxicity

Dose-limiting toxicities are defined as any adverse event with an onset within first 28 days following first dose of AMG 160 with any of the following criteria unless clearly attributable to causes other than AMG 160 treatment:

- grade 5 toxicity (eg, death not due to disease progression)
- grade 3 adverse event lasting more than 3 days (with the exception of fatigue)
- grade 4 adverse event regardless of duration

- grade 3 nausea, vomiting, or diarrhea that do not improve to grade ≤ 1 within 72 hours despite maximum supportive care
- grade ≥ 3 neurologic events that do not improve to grade ≤ 1 within 7 days with treatment interruption and routine medical management
- grade 3 febrile neutropenia that cannot be attributed to CRS
- AST or ALT values of $> 3 \times$ ULN AND with serum TBL level of $> 2 \times$ ULN without signs of cholestasis or there is no other clear alternative to explain the observed liver-related laboratory abnormalities (ie, criteria for Hy's Law indicative of severe drug-induced liver injury [DILI])
- grade 4 neutropenia lasting > 7 days
- grade 4 thrombocytopenia lasting > 7 days
- grade 3 or higher thrombocytopenia with clinically significant bleeding regardless of duration of thrombocytopenia
- grade 4 anemia
- grade 4 non-hematologic laboratory abnormality of any duration

The following adverse events will NOT be adjudicated as DLT regardless of the duration:

- lymphopenia or lymphocyte count decreased of any grade
- grade 3 fever (defined as a temperature $\geq 40^\circ\text{C}$ with a duration of ≤ 24 hours) occurring outside the context of CRS
- laboratory parameters of grade ≥ 3 , not considered clinically relevant, and improved to grade ≤ 2 within 72 hours.
- grade ≥ 3 transaminitis associated with CRS that resolves to grade ≤ 1 within 5 days

Determination of whether a subject is evaluable for DLT assessment will be made in accordance with the following rules:

- Subjects who receive study treatment and remain on study through the DLT assessment window will be considered DLT-evaluable.
- Subjects who do not complete safety assessments during the DLT assessment window for reasons other than a DLT will be considered nonevaluable for dose escalation decisions and MTD determination and may be replaced by an additional subject at that same dose level.

Subjects who receive supportive care during the DLT assessment window that confounds the evaluation of DLTs may be replaced at the discretion of the medical monitor or DLRT. See Section 9.4.1.1.1 for the stopping rules for siltuximab intervention.

6.2.2 Dosage Adjustments, Delays, Rules for Withholding or Restarting, Permanent Discontinuation

6.2.2.1 Amgen Investigational Product: AMG 160

The reason for dose change of AMG 160 is to be recorded on each subject's electronic case report form (eCRF).

For treatment interruptions, delays, and discontinuations, refer to AMG 160 guidance in [Table 6-3](#) in consultation with the Amgen medical monitor.

If any of the following events occur, further accrual will be suspended and a safety analysis conducted and submitted to FDA for review prior to resuming enrollment.

- any 1 treatment-related grade 5 adverse event or
- any 2 of the same treatment-related, clinically significant grade 4 adverse events at least possibly related to AMG 160

6.2.2.1.1 Infusion Interruptions/Delays/Withholding and Re-start in Case of Technical/Logistical Issues

Events leading to infusion interruption or delay for technical/logistical reasons may include: technical problem with the infusion pump or the investigational product is incorrectly prepared or administered.

Infusion Interruptions due to Technical/Logistical Issues

The administration of AMG 160 should not be interrupted for short-term (approximately 60 minute) or [REDACTED], if possible. In case of infusion interruption, due to any technical or logistic reason, the interruption should be as short as possible and the infusion continued at the earliest time possible.

[figure not shown]
In case of infusion interruption, immediately consult with Amgen medical monitor to determine if:

- investigational product stability is sufficient to administer the remaining infusion or
- a new infusion can be administered or
- the dose should be withheld

For short-term (approximately 60 minute) infusions, if the remaining infusion can be administered, no specific precautions have to be taken. If a new infusion can be administered, follow the procedures in the Schedule of Activities (see Section 1.3) or the cycle day on which the original (interrupted) infusion was administered. [REDACTED]

[REDACTED] If the

infusion will need to be withheld, follow the instructions for re-start after interruptions due to adverse events described below for the next infusion.

Any interruption of an infusion should be recorded in the eCRF, providing the start and stop date/time of the infusion if the interruption is > 2 hours.

Infusion Delay due to Technical/Logistical Issues

[figure not shown]
If the infusion delay was ≤ 72 hours, the dose can be administered without specific precautions. Procedures performed will follow the schedule of assessments for the cycle day on which the infusion was originally planned. The following infusion should then be administered after 14 (± 1) days; eg, if the day 8 infusion needs to be delayed for logistical issues, and could only be administered on day 10, the next infusion should be administered on day 24 (± 1 day) rather than the regular day 22. The ± 1 -day window is allowed until the original dosing schedule is met again.

If the delay of the next infusion was > 72 hours, the dose will need to be skipped and the instructions for re-start after interruptions due to adverse events described below should be followed.

6.2.2.1.2 Infusion Interruptions/Delays/Withholding and Re-start due to Adverse Events

6.2.2.1.2.1 General Guidelines

Subjects should be assessed for toxicity before each infusion of AMG 160. The severity of the toxicity will be graded using the CTCAE version 5.0, with the exception of CRS, which must be graded using the criteria referenced in the publication by Lee et al, 2014; TLS, which must be graded according to the Cairo Bishop criteria referenced in the publication by Coiffier et al, 2008; and immune-effector cell associated neurologic syndrome (ICANS) will be using the criteria referenced in the publication by Lee et al, 2019. Infusion modification and dose reduction due to a toxicity will be performed according to the instructions described below and outlined in [Table 6-3](#).

6.2.2.1.2.2 Infusion Interruptions due to Adverse Events

Events occurring during the infusion and requiring treatment interruption will be managed by immediate infusion interruption. The site should record any unscheduled interruption of an infusion on the eCRF and provide the start and stop date/time of the infusion.

Events requiring an infusion interruption are listed in [Table 6-3](#).

6.2.2.1.2.3 Delay of Subsequent Infusion due to Adverse Events

Events occurring after the end of the infusion and requiring a delay of treatment will be managed by delay of the subsequent infusion. The site should record any delay of an infusion on the eCRF and provide the start and stop date/time of the infusion.

Events requiring a delay of the subsequent infusion are listed in [Table 6-3](#).

Infusion interruptions or delays for other reasons need to be discussed with the Amgen medical monitor.

6.2.2.1.2.4 Re-start of Infusion

Re-starting treatment after an interruption/delay due to an adverse event or if the interruption/ delay was > 72 hours, regardless of the reason, should be performed under medical supervision. [REDACTED]

[REDACTED]. The following assessments should be performed as for days 1, 2, and 3 per the Schedule of Activities for cycle 1 (see Section [1.3](#)).

- vital signs, pulse oximetry
- physical examination
- neurological examination (only in case the treatment interruption was due to a neurologic event)
- weight
- ECOG
- safety labs (hematology, chemistry, coagulation, urinalysis)

The subject should be hospitalized for at least 48 hours after re-start of the infusion.

6.2.2.1.2.5 Dose Adjustments and Re-start at a Lower Dose Level

For adverse events for which restart of treatment is allowed according to the guidelines outlined in [Table 6-3](#), treatment may be resumed at the same or lower dose.

Re-start at a lower dose level:

In the following cases, the next infusion administered should be at the previous (lower) dose level:

If the event occurred during the infusion and caused an interruption of the infusion for more than 72 hours and therefore the affected dose was withheld, or

If the event started after the end of an infusion and administration of the next infusion had to be delayed for more than 72 hours due to the event.

For specific events as outlined in [Table 6-3](#).

[figure not shown]

In either case, re-escalation to the target dose can be considered for the next infusion if treatment at the lower dose has been well tolerated with no events requiring dose interruption or delay as described in [Table 6-3](#). After the dose re-escalation, the following assessments should be performed as for day 8 through day 11 per the Schedule of Activities for cycle 1 (see Section [1.3](#)).

- vital signs, pulse oximetry
- physical examination
- neurological examination (only in case the treatment interruption was due to a neurologic event)
- safety labs (hematology, chemistry, coagulation, urinalysis)

The subject should be hospitalized for at least 48 hours after re-escalation.

In case an additional dose de-escalation is required, permanently discontinue treatment.

Table 6-3. Infusion Interruptions/Delays/Withholding/Permanent Discontinuation and Management of Adverse Events Including Dose Reductions

Grade	Description of Severity	Interruption/Delay	Specific Management	Re-start guidance	Permanent Discontinuation
Infusion-related Reaction					
1	Mild transient reaction; infusion interruption not indicated; intervention not indicated	N/A	Consider medication to control infusion reaction as deemed appropriate by the investigator according to local standard of care and institutional guidelines.	N/A	N/A
2	Therapy or infusion interruption indicated but responds promptly to symptomatic treatment (eg, antihistamines, NSAIDs, narcotics, IV fluids); prophylactic medications indicated for ≤ 24 hours	Short-term infusion: Immediate interruption/delay until event has improved to grade ≤ 1 	Increase monitoring of vital signs as medically indicated until the subject is deemed medically stable	
 • Re-start possible, if successfully managed and improvement to ≤ grade 1 in ≤ 14 days. For short-term (approximately 60 minute) infusions, in case of infusion interruption, continue treatment with next scheduled infusion (do not resume prior infusion) 
 • Delay of the next infusion: 
 – < 7 days: administer the delayed infusion (as long as the next scheduled infusion is > 6 days from delayed infusion) and follow the schedule of assessments for the cycle day on which the infusion was originally planned. – > 7 days: skip the delayed infusion and resume schedule of assessments for the next scheduled infusion • Hospitalization: 48 hours • Dose modification: resume at the same dose or reduce to next lower dose, if clinically indicated • Additional measures:  and additional assessments as indicated in Section 6.2.2.1.2.4 	If subject missed more than 2 consecutive doses of AMG 160

Abbreviations and footnotes defined on last page of table.

Table 6-3. Infusion Interruptions/Delays/Withholding/Permanent Discontinuation and Management of Adverse Events Including Dose Reductions

Grade	Description of Severity	Interruption/Delay	Specific Management	Re-start guidance	Permanent Discontinuation
Infusion-related Reaction (continued)					
3	Prolonged (eg, not rapidly responsive to symptomatic medication and/or brief interruption of infusion); recurrence of symptoms following initial improvement; hospitalization indicated for clinical sequelae	Immediate interruption/ delay until event has improved to grade \leq 1	Consider supportive therapy including steroids as clinically indicated. Increase monitoring of vital signs as medically indicated until the subject is deemed medically stable.	
 As for grade 2 infusion-related reaction, with the exception of mandatory dose modification: reduce to next lower dose 	If subject missed more than 2 consecutive doses of AMG 160
4	Life-threatening consequences; urgent intervention indicated	N/A	As for grade 3 infusion-related reaction	N/A	Immediately stop the infusion (if applicable) and permanently discontinue AMG 160

Abbreviations and footnotes defined on last page of table.

Table 6-3. Infusion Interruptions/Delays/Withholding/Permanent Discontinuation and Management of Adverse Events Including Dose Reductions

Grade	Description of Severity ^a	Interruption/Delay	Specific Management	Re-start guidance	Permanent Discontinuation
Cytokine Release Syndrome					
1	Symptoms are not life-threatening and require symptomatic treatment only, eg, fever, nausea, fatigue, headache, myalgias, malaise	Avoid treatment interruption	Administer symptomatic treatment (eg, paracetamol/ acetaminophen for fever). Monitor for CRS symptoms including vital signs and pulse oximetry at least Q2 hours for 12 hours or until resolution, whichever is earlier.	N/A	N/A
2	Symptoms require and respond to moderate intervention 
 Grade 1 CRS symptoms, AND Oxygen requirement < 40%, OR Hypotension responsive to fluids or low dose of 1 vasopressor^b, OR Grade 2 organ toxicity or grade 3 transaminitis per CTCAE criteria 	Immediately interrupt/delay AMG 160 until event improves to CRS grade ≤ 1. [REDACTED]	Administer: 
 Symptomatic treatment (eg, paracetamol/ acetaminophen for fever) Supplemental oxygen when oxygen saturation is < 90% on room air Intravenous fluids or low dose vasopressor for hypotension when systolic blood pressure is < 85 mmHg. Persistent tachycardia (eg, > 120 bpm) may also indicate the need for intervention for hypotension. Monitor for CRS symptoms including vital signs and pulse oximetry at least Q2 hours for 12 hours or until resolution to CRS grade ≤ 1, whichever is earlier. For subjects with extensive co-morbidities or poor performance status, manage per grade 3 CRS guidance below. Persistent tachycardia with complications (eg, atrial fibrillation) should be managed with rate control medications (eg, metoprolol) along with cardiology consultation. [REDACTED]	
 Re-start possible if successfully managed and improved to ≤ grade 1 within 7 days. Consult with Amgen medical monitor first. In case of infusion interruption, continue treatment with next planned dose (do not resume prior infusion). Delay of next infusion: 
 < 7 days: administer the delayed infusion (as long as the next scheduled infusion is > 6 days from delayed infusion) and follow the schedule of assessments for the cycle day on which the infusion was originally planned. > 7 days: skip the infusion and resume schedule of assessments for the next scheduled infusion Hospitalization: 48 hours Dose modification: resume at the same dose or reduce to next lower dose, if clinically indicated Additional measures: [REDACTED] and additional assessments as indicated in Section 6.2.2.1.2.4 	If there is no improvement to CRS ≤ grade 1 within 7 days OR If subject missed more than 2 consecutive doses of AMG 160

Abbreviations and footnotes defined on last page of table.

Table 6-3. Infusion Interruptions/Delays/Withholding/Permanent Discontinuation and Management of Adverse Events Including Dose Reductions

Grade	Description of Severity ^a	Interruption/Delay	Specific Management	Re-start guidance	Permanent Discontinuation
Cytokine Release Syndrome (continued)					
3	Symptoms require and respond to aggressive intervention 
 • Grade 1 CRS symptoms, AND • Oxygen requirement \geq 40%, OR • Hypotension requiring high-dose^b or multiple vasopressors, OR • Grade 3 organ toxicity or grade 4 transaminitis per CTCAE criteria 	Immediately interrupt / delay AMG 160 until event improves to CRS grade \leq 1.	Admit to intensive care unit for close clinical and vital sign monitoring per institutional guidelines (unless related to asymptomatic elevation of liver enzymes). Administer [REDACTED] (or equivalent) IV at a dose maximum of 3 doses of 8 mg (24 mg/day). The dose should then be reduced step-wise. AND/OR Investigators should also consider use of tocilizumab ^{c,d,e} as an additional therapy in this setting at a dose of 4 - 8 mg/kg IV as a single dose. Persistent tachycardia with complications (eg, atrial fibrillation) should be managed with rate control medications (eg, metoprolol) along with cardiology consultation. [REDACTED]	
 • Re-start possible if successfully managed and improved to \leq grade 1 within 7 days. • Consult Amgen medical monitor. • In case of infusion interruption, continue treatment with next planned dose (do not resume prior infusion). • Delay of next infusion: 
 – < 7 days: administer the delayed infusion (as long as the next scheduled infusion is > 6 days from delayed infusion) and follow the schedule of assessments for the cycle day on which the infusion was originally planned. – > 7 days: skip the infusion and resume schedule of assessments for the next scheduled infusion • Hospitalization: 48 hours • Dose modification: reduce to next lower dose (continuation at same dose with [REDACTED] may be allowed – consult with medical monitor) Additional measures: [REDACTED] and additional assessments as indicated in Section 6.2.2.1.2.4	If there is no improvement to CRS \leq grade 1 within 7 days. OR If subject missed more than 2 consecutive doses of AMG 160 Decision to discontinue should be made in consultation with Amgen medical monitor.

Abbreviations and footnotes defined on last page of table.

Table 6-3. Infusion Interruptions/Delays/Withholding/Permanent Discontinuation and Management of Adverse Events Including Dose Reductions

Grade	Description of Severity ^a	Interruption/Delay	Specific Management	Re-start guidance	Permanent Discontinuation
Cytokine Release Syndrome (continued)					
4	Life-threatening symptoms 
 • Grade 1 CRS symptoms, AND • Requirement for ventilator support OR • Grade 4 organ toxicity (excluding transaminitis) per CTCAE criteria 		Admit to intensive care unit for close clinical and vital sign monitoring per institutional guidelines. Administer [REDACTED] (or equivalent) IV at a dose maximum of 3 doses of 8 mg (24 mg/day). Further corticosteroid use should be discussed with the Amgen medical monitor. Additionally, tocilizumab ^{c,d,e} should be administered if regionally available at a dose of 4 - 8 mg/kg as a single dose and may be repeated once within 24 to 48 hours based on clinical assessment. Persistent tachycardia with complications (eg, atrial fibrillation) should be managed with rate control medications (eg, metoprolol) along with cardiology consultation. [REDACTED]	N/A	Immediately stop the infusion (if applicable) and permanently discontinue AMG 160

Abbreviations and footnotes defined on last page of table.

Table 6-3. Infusion Interruptions/Delays/Withholding/Permanent Discontinuation and Management of Adverse Events Including Dose Reductions

Grade	Interruption/Delay	Specific Management	Re-start guidance	Permanent Discontinuation
Tumor Lysis Syndrome (TLS) – Grading according to Cairo-Bishop Criteria				
2 (clinical TLS)	Immediate interruption/ delay until event has improved to grade ≤ 1	TLS should be managed according to the local standard of care and institutional guidelines.	
 • Re-start possible if successfully managed and improvement to \leq grade 1 in ≤ 14 days • Consult Amgen medical monitor. • In case of infusion interruption, continue treatment with next schedule infusion (do not resume prior infusion). • Delay of next infusion: 
 – < 7 days: administer the delayed infusion (as long as the next scheduled infusion is > 6 days from delayed infusion) and follow the schedule of assessments for the cycle day on which the infusion was originally planned. – > 7 days: skip the infusion and resume schedule of assessments for the next scheduled infusion • Hospitalization: 48 hours • Dose modification: reduce to next lower dose • Additional measures: [REDACTED] and additional assessments as indicated in Section 6.2.2.1.2.4 	
If subject missed more than 2 consecutive doses of AMG 160
 
OR
 
In case of repeat grade 2 TLS event despite dose reduction.

